### 3.6.1.3 Ramucirumab exposure

The dose information will be assessed by the following:

- Total number of cycles started.
- Number of cycles started per participant.
- Duration of ramucirumab exposure (in weeks) is defined by date of last administration of ramucirumab + number of theoretical days until the next administration date of first administration of ramucirumab/7.
- Actual dose (in mg/kg). In case of dose interruption, actual dose will be the sum of the actual doses administered before and after the dose interruption.
- Cumulative dose (mg/kg): the cumulative dose is the sum of all actual doses of ramucirumab, given from first to last administration.
- Actual dose intensity (ADI in mg/kg/week): defined as the cumulative dose divided by the duration of ramucirumab exposure (in weeks).
- Planned dose intensity (PDI in mg/kg/week): corresponds to the planned dose multiplied by the theoretical total number of doses started and divided by the theoretical cycle duration expressed in weeks (ie, 2 weeks per cycle started). Note: Theoretical total number of doses started is derived based on cycles where at least one IMP is administered (even in case of dose omission), up to the end of treatment of ramucirumab.
- Relative dose intensity (RDI, in %):100  $\times \frac{\text{ADI (mg/kg/week)}}{\text{PDI (mg/kg/week)}}$ .

The total number of cycles started, number of cycles started by participant will be summarized as a quantitative variable and by category (number [%] of participants receiving at least 1 cycle, at least 2 cycles, etc). Duration of ramucirumab exposure, cumulative dose, ADI and RDI will be summarized quantitatively.

The following variables will be derived to describe dose modifications and dose interruptions:

• Dose reduction: The first administration will not be counted as a dose reduction. For the second and subsequent ramucirumab administrations, dose reduction will be determined using the dose level intervals provided in Table 6, by comparing the current dose level to the previous dose level. If the current dose level is below the dose level interval of the previous dose administration, then the current dose level is considered reduced.

Actual dose level	Dose level interval
Starting dose (8 mg/kg)	>7 mg/kg
Dose level -1 (6 mg/kg)	>5.5 mg/kg and ≤7 mg/kg
Dose level -2 (5 mg/kg)	> 4 mg/kg and ≤5.5 mg/kg
Low dose	>0 mg/kg and ≤4 mg/kg

#### Table 6 - Ramucirumab dose reduction criteria

- Dose delay: A dose will be considered as delayed if the ramucirumab administration date of the current cycle 14 days ramucirumab administration date of the previous cycle is >2 days. Dose delay is not defined for the first cycle.
- Dose omission is defined as a dose not administered at the scheduled visit but administered afterwards.
- Dose interruption: A dose will be considered as interrupted if the ramucirumab administration is stopped during an infusion regardless of whether it is restarted or not.

Dose modifications and dose interruptions will be analyzed by participant and cycle as follows:

- **Participant** (number of participants treated will be used as denominator)
  - Number (%) of participants with at least 1 dose modification
    - Number (%) of participants with at least 1 dose delayed
    - Number (%) of participants with at least 1 dose reduction
    - Number (%) of participants with at least 1 dose omission
  - Number (%) of participants with a least 1 dose interruption
- Cycle (number of cycles started will be used as denominator)
  - Number (%) of cycles with at least 1 dose modification
    - Number (%) of cycles with at least 1 cycle delayed
    - Number (%) of cycles with at least 1 dose reduction
    - Number (%) of cycles with at least 1 dose omission
  - Number (%) of cycles with at least 1 dose interruption

# 3.6.2 Adverse events

# General common rules for adverse events

All AEs will be graded according to NCI-CTCAE Version 5.0 and coded to a lower-level term (LLT), preferred term (PT), high-level term (HLT), high-level group term (HLGT), and associated primary system organ class (SOC) using the Medical Dictionary for Regulatory Activities (MedDRA) version currently in effect at Sanofi at the time of database lock.

The AEs will be analyzed in the following 3 categories:

- Pre-treatment AEs: AEs that developed, worsened, or became serious during the pre-• treatment period.
- TEAEs: AEs that developed, worsened, or became serious during the treatment-emergent • period
- Post-treatment AEs: AEs that developed, worsened, or became serious during the posttreatment period

Similarly, the deaths will be analyzed in the pre-treatment, treatment-emergent, and posttreatment periods.

The primary AE analyses will be on TEAEs. Pre-treatment and post-treatment AEs will be described separately.

An AE with incomplete or missing date/time of onset (occurrence, worsening, or becoming serious) will be classified as a TEAE unless there is definitive information to determine it is a pretreatment or a post-treatment AE.

If the assessment of the relationship to IMP is missing for an AE, this AE will be assumed as related to IMP. A missing grade will be left as missing.

Multiple occurrences of the same event in the same participant will be counted only once in the tables within a treatment phase, using the maximum (worst) grade by treatment phase. Summaries will be provided for all grades combined and for Grade  $\geq 3$  (including Grade 5). Missing grades, if any, will be included in the "all grades" category.

The AE tables will be sorted as indicated in Table 7.

AE presentation	Sorting rules
SOC, HLGT, HLT, and PT	By the internationally agreed SOC order and by alphabetic order of HLGTs, HLTs, and PTs.
SOC and PT	By the internationally agreed SOC order and decreasing frequency of PTs a, b
PT	By decreasing frequency of PTs a
a Sorting will be based on the	SAR408701 overall incidence

#### Table 7 - Sorting of AE tables

ed on the SAR408701 overall incidence

b The table of all TEAEs presented by primary SOC and PT will define the presentation order for all other tables (eg, treatment-emergent SAE) presented by SOC and PT, unless otherwise specified.

#### Analysis of all adverse events

The overview of TEAE with the details below will be generated:

- Any TEAE
- Any Grade ≥3 TEAE
- Grade 5 TEAE (any TEAE with a fatal outcome during the treatment-emergent period)

- Any treatment-emergent SAE
- Any treatment-emergent adverse event of special interest (AESI)
- Any TEAE leading to permanent full study intervention discontinuation
- Any TEAE leading to permanent partial discontinuation of tusamitamab ravtansine
- Any TEAE leading to permanent partial discontinuation of ramucirumab
- Any TEAE related to IMP
- Any Grade  $\geq$ 3 TEAE related to IMP
- Any serious TEAE related to IMP
- Any treatment-emergent corneal event (CMQ "Corneal events compound level")
- Any treatment-emergent peripheral neuropathy event TEAE (SMQ "Peripheral neuropathy" [Narrow and Broad])
- Any ocular/visual symptoms TEAE (CMQ "Eye disorders exclude corneal disorders")

The AE summaries of Table 8 will be generated with number (%) of participants experiencing at least 1 event. The analyses will be performed for all grades combined and for Grade  $\geq$ 3.

Type of AE	MedDRA levels
AII TEAE	Primary SOC, HLGT, HLT and PT
	Primary SOC and PT
	PT
TEAE related to IMP as per Investigator's judgment	Primary SOC and PT
TEAE related to tusamitamab ravtansine as per Investigator's judgment	Primary SOC and PT
TEAE related to ramucirumab as per Investigator's judgment	Primary SOC and PT
Treatment-emergent SAE	Primary SOC, HLGT, HLT and PT
	Primary SOC and PT
Treatment-emergent SAE related to IMP as per Investigator's judgment	Primary SOC and PT
Treatment-emergent SAE related to tusamitamab ravtansine as per Investigator's judgment	Primary SOC and PT
Treatment-emergent SAE related to ramucirumab as per Investigator's judgment	Primary SOC and PT
TEAE leading to permanent full study intervention discontinuation	Primary SOC and PT
TEAE leading to permanent partial discontinuation of tusamitamab ravtansine	Primary SOC and PT
TEAE leading to permanent partial discontinuation of ramucirumab	Primary SOC and PT

#### Table 8 - Analyses of adverse events

Type of AE	MedDRA levels
TEAE leading to death b	Primary SOC and PT
TEAE related to tusamitamab ravtansine and leading to death $^{b}$	Primary SOC and PT
TEAE related to ramucirumab and leading to death b	
AE leading to death b	
- In context of disease progression c	
- In context other than disease progression d	
Pretreatment AE	Overview a
	Primary SOC and PT
Pre-treatment SAE	Primary SOC and PT
Post-treatment AE	Overview a
	Primary SOC and PT
Post-treatment SAE	Primary SOC and PT
TEAE leading to dose modification of tusamitamab ravtansine (including dose delay, dose reduction and dose omission)	Primary SOC and PT
TEAE leading to dose modification of ramucirumab (including dose delay, dose reduction and dose omission)	Primary SOC and PT
TEAE leading to dose interruption of tusamitamab ravtansine	Primary SOC and PT
TEAE leading to dose interruption of ramucirumab	Primary SOC and PT

a Will include the following AE categories: any AEs, any serious AEs, any AEs leading to death, any AEs leading to permanent full study intervention discontinuation (except for pretreatment)

b Death as an outcome of the AE as reported by the Investigator in the AE page

c Death within 30 days from last IMP administration and the cause of death is disease progression

*d* Death within 30 days from last IMP administration and for whom cause of death is not disease progression or the death occurred more than 30 days from last IMP administration and the cause of death is AE

# Analysis of deaths

In addition to the analyses of deaths included in Table 8 the number (%) of participants in the following categories will be provided:

- Deaths during the treatment-emergent and post-treatment periods by study period and reason for death
- An overview of Grade 5 AEs will be provided with the following categories:
  - Grade 5 AE (TEAE and post-treatment).
  - Fatal TEAE (regardless of date of death/period).
    - Grade 5 TEAE with a fatal outcome during the treatment period,
    - Any Grade TEAE with a fatal outcome during the posttreatment period.
  - Post-treatment Grade 5 AE (excluding a TEAE that worsened to Grade 5 during the post-treatment period).
- Deaths in non-enrolled participants or enrolled but not treated participants.

#### Analysis of adverse events of special interest (AESIs) and other AEs of interest

AESIs and other AEs of interest will be selected for analyses as indicated in Table 9. Number (%) of participants experiencing at least 1 TEAE will be provided overall for AESIs, and for each other event of interest, by SOC and PT (if applicable). DLT observed during the DLT observation period will be listed in the DLT-evaluable population. Tables will be sorted as indicated in Table 7.

AESIs and other AEs of interest	Selection				
AESIs					
Grade ≥3 keratopathy	e-CRF AESI specific tick box on the AE page. It could include Grade ≥3 events with PTs from CMQ of corneal events				
Bundle branch blocks or any conduction defect	e-CRF AESI specific tick box on the AE page. It could include events with PTs from SMQ "Conduction defects" (Narrow)				
Grade ≥3 liver enzyme increased (symptomatic or asymptomatic)	e-CRF AESI specific tick box on the AE page. It could include Grade ≥3 PTs from the SMQ "Hepatic disorders" (Narrow and Broad)				
Symptomatic overdose (serious or nonserious) with IMP/NIMP	e-CRF symptomatic overdose specific tick box on the Overdose page.				
Pregnancy of a female participant entered in a study as well as pregnancy occurring in a female partner of a male participant entered in a study with IMP/NIMP	e-CRF specific tick box for AE linked to pregnancy on the Pregnancy page.				
DLT during DLT observation period	e-CRF specific DLT page				
Other AEs of interest					
Any AE meeting DLT criteria beyond DLT observation period	AEs reported on the e-CRF specific DLT page outside the DLT observation period				
Corneal events (reported as AEs)	CMQ "Corneal events compound level" containing the PTs included in both SOC "Eye disorders" and SMQ "Corneal disorders" (Narrow)				
Ocular/visual adverse events (excluding corneal disorders)	CMQ "Eye disorders exclude corneal disorders" containing the PTs included in SOC "Eyes disorders" and excluding PTs in SMQ "Corneal disorders" (Narrow)				
Cardiac conduction defects	SMQ "Conduction defects" (Narrow)				
Peripheral neuropathy events	SMQ "Peripheral neuropathy" (Narrow and Broad)				
Colitis events (excluding infective)	CMQ "Colitis (excluding infective)" containing PTs included in HLT "Colitis (excl infective)")				
Hypersensitivity events	SMQ "Hypersensitivity" (Narrow) and adverse event occurring on the day or the day after the infusion				
Hepatic disorders adverse events	SMQ "Hepatic disorders" (Narrow and Broad)				
Hematological adverse events	SMQ "Haematopoietic cytopenias" (Narrow and Broad)				
AE related to COVID-19 illness	SMQ "COVID-19" (Narrow)				

#### Table 9 - Selections for AESIs and other AEs of interest

An overview of corneal TEAEs will be provided with the following AE categories: any corneal TEAEs, Grade  $\geq$ 3 corneal TEAEs, treatment-emergent corneal SAEs, corneal TEAEs related to IMP, Grade  $\geq$ 3 corneal TEAEs related to IMP, corneal TEAEs leading to permanent full intervention discontinuation, corneal TEAEs leading to permanent partial discontinuation of tusamitamab ravtansine, and corneal TEAEs leading to dose modification (cycle delay, dose reduction, or dose omission) of tusamitamab ravtansine.

A summary of treatment-emergent corneal events will be provided.

- Cycle of first occurrence regardless of the grade
- Cycle of first occurrence of the worst grade
- Number (%) of participants by worst grade
- Relationship to study intervention: in case of multiple occurrences in a single participant with different relationships, if any event is related, then the relationship will be considered as related for that participant
- Action taken with the study intervention: in case of multiple occurrences with different actions in a single participant, the most severe action taken will be tabulated and selected according to the following order of severity: drug withdrawn, dose reduced, drug interrupted, dose not changed
- Outcome: in case of multiple occurrences with different outcomes in a single participant, the most severe outcome will be tabulated and selected according to the following order of severity: fatal, not recovered or resolved, recovering and resolving, recovered and resolved with sequelae, recovered and resolved, unknown.

In addition, analyses on occurrence and recurrence of corneal events will be provided. An occurrence of a corneal event will be defined as 1 or a group of concomitant corneal events. A recurrence will be defined as any occurrence of corneal event starting after a previously resolved occurrence.

- The number of occurrences by participant
- The time to first onset of corneal event will be described using Kaplan-Meier curves. Time to first onset is defined as the time from the date of first IMP administration to the date of the first occurrence of the event. In the absence of an event before the analysis cut-off date, it will be censored at the end date of the treatment-emergent period, analysis cut-off date, or date of death, whichever occurs first.
- The time to recovery will be summarized using descriptive statistics in participants who have had at least 1 recovered or resolved occurrence of a corneal event (with or without sequelae), considering the longest duration among all occurrence by participant.
- The time to recurrence will be summarized using descriptive statistics in participants who have had at least one recurrence, considering the shortest time among all recurrences by participant.

Beside the AE categorized as ocular/visual adverse events, all ocular symptoms (coded term) recorded in e-CRF will be reported as descriptive analysis. Same descriptive analysis will be done separately for ocular/visual symptoms associated to treatment-emergent corneal events (CMQ).

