# 3.6 OTHER SAFETY ANALYSES

All safety analyses will be performed on the all-treated population as defined in Section 2, by dose level (if applicable) and overall, unless otherwise specified, using the following common rules:

- The analysis of the safety variables will be essentially descriptive, and no testing is planned.
- Safety data in participants who do not belong to the all-treated population (eg, treated but not enrolled) will be provided.

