#### Visual acuity test

Analyses are done on the best corrected visual acuity (BCVA) assessed using Snellen Chart method.

Frequency tables on BCVA measured during the on-treatment period will be performed separately on all participants and on participants who experienced at least one treatment-emergent corneal event:

- On the worst change from baseline: No worsening versus baseline (no line decrease), Worsening versus baseline (1 to 3 lines decrease versus baseline, or >3 lines decrease versus baseline).
- On the worst absolute value: No change versus baseline, Worsening versus baseline (BCVA equals to 20/40 or better, BCVA worse than 20/40 up to 20/200, BCVA 20/200 or worse).
- On the CTCAE worst vision decrease: BCVA equals to 20/40 or better or 1 to 3 lines decrease versus baseline, BCVA worse than 20/40 up to 20/200 or >3 lines decrease versus baseline, BCVA 20/200 or worse.

• For participants who had worsening versus baseline (at least one line decrease) on BCVA, the worst outcome on the last BCVA will be displayed: Recovered to baseline, Not recovered to baseline, Lost to follow-up or dead with ongoing corneal events.

A participant will be considered as lost to follow-up if the participant discontinued the study and did not perform any follow-up visit.

A shift table of the category of the last BCVA value (Normal (20/20 or better), worse than 20/20 up to 20/40, worse than 20/40 up to 20/200 or 20/200 or worse) versus the category of the worst BCVA value (20/40 or better, worse than 20/40 up to 20/200, 20/200 or worse) will be performed for participants who experienced at least one treatment-emergent corneal event.

For the summary table on participants who experienced at least one treatment-emergent corneal event, the worst value and the worst change from baseline are measured during any of the treatment-emergent corneal events experienced by the participant (between start date and end date of the corneal events). For summary table on all participants, all on-treatment BCVA values are considered.

The worst classification between the laterality will be considered for the worst absolute value, the worst change from baseline and the last value separately even if not measured on the same eye. If the worst absolute value is the same for both eyes, then the eye with the worst change from baseline is considered, and if identical, then the eye with the worst last value is considered.

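### The corneal-event outcome ranking in SAP 3.6.2 puts unknown below full recovery, so a recovered occurrence hides one whose outcome was never established

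*SAP*

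**What the plan says.** The rule is in SAP 3.6.2, in the summary of treatment-emergent corneal events that follows Table 9. It applies under this condition: "Outcome: in case of multiple occurrences with different outcomes in a single participant". In that case "the most severe outcome will be tabulated and selected according to the following order of severity: fatal, not recovered or resolved, recovering and resolving", and the list closes with "recovered and resolved with sequelae, recovered and resolved, unknown".

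The entry just above it, on action taken, uses the same construction and runs "drug withdrawn, dose reduced, drug interrupted, dose not changed", from the gravest action to the mildest. Both lists are therefore in descending severity, and *unknown* holds the least severe of six ranks. Nothing else in the SAP or protocol overrides this for the corneal outcome row.

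**The concern.** A table said to show each participant's most severe outcome should not report recovery when one of that participant's events has no established outcome. Here it can.

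Protocol 2.3.1 names corneal toxicity as the main identified risk of tusamitamab ravtansine and describes it as reversible. The outcome row is one of the places where a reader will look to check that description. An error that runs only in the favourable direction is unwelcome there, even in a descriptive table.

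The rule also sits oddly beside two others in the same section. On missing causality the SAP says: "If the assessment of the relationship to IMP is missing for an AE, this AE will be assumed as related to IMP". And in the corneal summary itself, one related occurrence makes the whole participant related. Both settle doubt unfavourably, whereas the outcome ranking absorbs it into recovery.

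**Working it through.** The plan gives no figure to reproduce. The check is to apply the rule as written.

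**Ranks (SAP 3.6.2):** 1 fatal; 2 not recovered; 3 recovering; 4 recovered with sequelae; 5 fully recovered; 6 unknown. The tabulated outcome is the lowest rank number among the participant's occurrences.

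**Each known outcome paired with unknown:**

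- fatal + unknown: min(1, 6) = 1, shown as fatal
- not recovered + unknown: min(2, 6) = 2, shown as not recovered
- recovering + unknown: min(3, 6) = 3, shown as recovering
- recovered with sequelae + unknown: min(4, 6) = 4, shown as recovered with sequelae
- fully recovered + unknown: min(5, 6) = 5, shown as fully recovered
- unknown only: 6, shown as unknown

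In the first four pairs a documented outcome short of full recovery is still shown. The fifth is the problem: the row reports complete recovery while one event is unaccounted for.

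**Effect of moving unknown.** Six outcomes give 6 × 5 / 2 = 15 possible pairs.

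- Between *recovered with sequelae* and *fully recovered*: two neighbouring ranks swap, so 1 of 15 pairs changes (fully recovered + unknown becomes unknown).
- Directly above *recovered with sequelae*: 2 of 15 change, the second being sequelae + unknown.
- Directly below *not recovered*: 3 of 15 change, the third being recovering + unknown.

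**Size per affected participant, if there is one.** This needs an assumed number of participants with corneal events among the 32 to 38 to be treated, and an assumed denominator, which the SAP does not state.

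- Rate from protocol Table 2 (51 of 160, monotherapy at 100 mg/m² every 2 weeks): 32 × 51/160 = 10.2 and 38 × 51/160 = 12.1. One participant is then 1/12.1 to 1/10.2, about 8 to 10 percentage points.
- Loading-dose monotherapy in protocol 2.3.1: of 13 participants, 4 had keratopathy and 4 had keratitis, overlap not stated. On those two terms the rate lies between 4/13 and 8/13. That gives 32 × 4/13 = 9.8 up to 38 × 8/13 = 23.4 participants, so one is about 4 to 10 points.
- If percentages are taken over all treated participants instead: 1/38 to 1/32, about 2.6 to 3.1 points.

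These figures are conditional on one affected participant. They are not an expected bias, because neither document gives a rate of unknown outcomes or of recurrence.

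**The case against.** Ranking unknown last can be defended as a convention that known data take precedence over missing data. The SAP is not uniformly conservative: under the same general rules for adverse events, a missing grade is left missing and counted only under all grades. The contrast with the missing-causality rule is therefore suggestive rather than decisive. But the SAP does not state such a convention for outcomes, and it describes the rule as selecting the most severe outcome, which is how readers will take the table.

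The protocol also works to keep unknown outcomes few. Events of special interest and drug-related events still open at the end of treatment are followed to resolution or stabilization (protocol 4.1 and the follow-up note to the study flow chart). Symptomatic eyes are examined weekly until Grade 1, unless an ophthalmologist advises less often, and then at each cycle until full resolution (8.2.7.2). Complete ocular tests are repeated at end of treatment (8.2.2). This stands, and it is a good reason to expect little effect.

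Reversibility is also reported elsewhere. The visual-acuity outcome in SAP 3.6.3.2 uses "Recovered to baseline, Not recovered to baseline, Lost to follow-up or dead with ongoing corneal events", so it keeps loss to follow-up separate. However, it covers only participants whose acuity worsened. The time-to-recovery summary admits a participant on the strength of a single recovered occurrence. These outputs limit misreading but do not correct the outcome row.

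Finally, SAP 3.6 states: "The analysis of the safety variables will be essentially descriptive, and no testing is planned". That limits the consequence, and the point is graded accordingly.

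**Conclusion.** The point holds as a minor defect in a stated rule. A participant whose corneal occurrences are a mix of fully recovered and unknown is counted as recovered, and the resulting error can only favour recovery. It requires at least two occurrences, at least one unknown and all the rest fully recovered. The number of such participants is not estimable from the documents and may be zero. Neither primary endpoint is touched.

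A reader might infer more: that corneal events are expected to recur, that unknown outcomes gather in participants lost after their last episode, and that the recovered percentage is therefore inflated by 8 to 10 points. The documents do not support this. Protocol Appendix 6 sets contingency rules for second and third episodes but gives no recurrence rate. Neither document says how often outcomes are unknown or why. The 8 to 10 points is what one affected participant would contribute under one assumed event rate and one assumed denominator.

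**What to change.** In SAP 3.6.2, move *unknown* to sit between *recovered with sequelae* and *fully recovered*. Full recovery then no longer masks an unknown outcome, and unknown does not mask documented sequelae. Moving it higher, for example directly below *not recovered*, would hide known sequelae or a recovering event behind unknown, and should be avoided.

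Instead of this, or in addition, report the number of participants with any corneal occurrence of unknown outcome. That count also brings out unknown occurrences in participants already shown in a worse category, which no single-outcome ranking can do.

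The cost is one term moved in a list and, if wanted, one extra table row. No new data are needed. The recovered percentage may be slightly less favourable.
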